### 10.2 Statistical Analysis Plan (SAP)

#### 10.2.1 Descriptive Statistical Summary

A descriptive statistical summary will be provided for Investigator Quartile Improvement Score (IQIS, 0-4), tolerability parameters, VAS scores, and biopsy parameters. The descriptive statistical summary includes the N, mean, median, SD, MIN, and MAX of scores/values at all applicable time points.

Counts and percentages will be provided for Investigator Quartile Improvement Score (rating), SAE parameters, tolerability parameters, VAS (in category), and individual response data (GAIS and subject satisfaction).

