### 4. STUDY DESIGN AND ENDPOINTS

#### 4.1 Description of Study Design:

This is a prospective, non-randomized study of up to 30 subjects designed to assess the safety and effectiveness of a non-ablative fractional combination laser wavelength procedure for general resurfacing of photoaged skin. All study subjects will be treated on the whole face with the with the CLEAR + BRILLIANT TOUCH® diode laser 1927-nm & 1440-nm handpieces. Subjects will be treated with a consecutive series of four (4) treatments spaced 1-month apart, along with follow-up study visits at one (1) and three (3) months after final treatment. As primary and secondary effectiveness endpoints aim to evaluate improvement in photoaging damage post-treatment as compared to baseline following treatment with the FDA-cleared CLEAR + BRILLIANT TOUCH® System, no control group will be utilized.

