### 4.2.3 Safety Endpoints

Serious Adverse Events (SAEs) related and unrelated to the treatment procedure or to the CLEAR + BRILLIANT TOUCH® diode laser.

The severity of post-treatment skin responses:

- Immediate post-treatment erythema and edema (Visits: 1 and or 2 if screening and treatment on same day, Visits 3, 4 and 5)
- Prolonged post-treatment erythema, edema, dryness/flakiness, hypopigmentation, hyperpigmentation, blistering, scarring. (Visits 6 & 7)

The evaluation of pain and discomfort immediately after the treatment (within 60 minutes) as reported by the subject on a visual analog scale (VAS).

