#### 7.4 Visual Analog Scale (VAS)

The study subjects will be asked to complete an eleven point visual analog scale (VAS, 0-10) for the level of pain and discomfort associated with the study procedure to be completed by the subjects on the day of the procedure immediately after or within 60 minutes from the end of the procedure and recorded in the CRF treatment record. They may verbally respond with a numeric pain score.

Scoring will be reported by the provider on the treatment record.

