### 8. ASSESSMENT OF SAFETY

### 8.1 Specification of Safety Parameters

- Post-treatment skin responses, side effects (e.g., erythema, edema) will be scored by the study investigators, as appropriate, using a scale of 0 to 3 (none to marked), immediately after treatment, for each treatment.
- Side effects (prolonged erythema, edema, skin darkening or lightening in the treatment area, scarring, dryness/flakiness, blistering) will be scored, using a scale of 0 to 3 (none to marked), by study investigators at the beginning of every subsequent treatment, and at all follow-up visits.
- Subject's will log post-treatment skin responses, side effects (e.g., erythema, edema) using a scale of 0 to 3 (none to marked), after each treatment for seven (7) days in the patient diary.
- In addition, study subjects will be instructed to report all complications experienced post study procedure to the site personnel as soon as they occur/are observed.
- It is the Investigator's responsibility to determine seriousness, severity, and relatedness of the Adverse Event to the device and the procedure using the definitions below.

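### No planned table gives the share of treated subjects with a moderate or marked skin reaction at any of the four treatments, a share that can be 1 to 4 times the per-treatment percentage

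*Combined protocol and SAP*

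**What the plan says.** The intervention is a series (Section 4.1): "Subjects will be treated with a consecutive series of four (4) treatments spaced 1-month apart". Section 4.2.3 makes "The severity of post-treatment skin responses" a safety endpoint, together with pain after treatment.

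Section 8.1 sets out three streams of skin-response data:

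- Immediate responses, scored by the investigator "using a scale of 0 to 3 (none to marked), immediately after treatment, for each treatment".
- Later side effects on the same scale, scored "by study investigators at the beginning of every subsequent treatment, and at all follow-up visits".
- Subject ratings recorded "after each treatment for seven (7) days in the patient diary".

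Pain is rated on an "eleven point visual analog scale (VAS, 0-10) for the level of pain and discomfort" (Section 7.4), and the schedule of events places it at all four treatment visits.

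For analysis, Section 10.2.1 states "The descriptive statistical summary includes the N, mean, median, SD, MIN, and MAX of scores/values at all applicable time points". It then adds "Counts and percentages will be provided for Investigator Quartile Improvement Score (rating), SAE parameters, tolerability parameters, VAS (in category"), followed by the subject response data. Section 10.1 sets the denominator of percentages to subjects with non-missing data at the visit concerned, unless otherwise indicated, and permits removal from the analysis in the case of an adverse event. The Statistical Analysis Plan Table enters NA for tolerability and VAS and says only that lower scores are better. Sections 4.2.3, 8.1, 10.1 and 10.2 define no worst score per subject and no any-treatment incidence.

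**The concern.** Someone considering the series needs the chance of a moderate or marked reaction at some point in it. The planned tables answer a different question: what share reacted at a given treatment. They cannot be added up to the first quantity, because they do not show whether the reactors at one treatment are the same people as at the next. The same two subjects reacting four times, and eight subjects reacting once each, produce identical tables.

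No other planned output closes the gap. Section 8.2 has all adverse events recorded, but Section 10.2 names only serious adverse events for tabulation. The removal rule in Section 10.1 adds to the problem, since a subject with a strong reaction could be taken out of the analysis because of it.

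**Working it through.** The plan states no reaction rate, so there is no figure of its own to reproduce. The inputs from the documents are k = 4 treatments (Section 4.1) and up to 30 subjects (Section 5.2). The per-treatment shares p and the within-subject correlations below are assumptions.

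**1. Bounds.** Let p be the share reacting at each treatment, taken as equal across treatments, with every subject treated and scored four times.

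- Lower bound, same subjects each time: p, a ratio of 1.
- Upper bound, no subject reacts twice: min(1, 4p). The ratio is 4 only if 4p is at most 1, that is, p is at most 25%. At p = 50% the largest possible ratio is 1/0.50 = 2.

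**2. Between the bounds.** Independence gives 1 − (1 − p)^4; for example, 1 − 0.95^4 = 18.5% and 1 − 0.90^4 = 34.4%. For positive correlation, each subject is given an underlying normal tendency to react with an equal correlation rho between treatments. Entries are the share affected at any of the four treatments, with the ratio to p in brackets.

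| p | same subjects | rho 0.7 | rho 0.5 | rho 0.3 | independent | no repeats |
|---|---|---|---|---|---|---|
| 5% | 5% (1) | 12.0% (2.4) | 14.4% (2.9) | 16.4% (3.3) | 18.5% (3.7) | 20% (4) |
| 10% | 10% (1) | 21.7% (2.2) | 25.9% (2.6) | 29.5% (3.0) | 34.4% (3.4) | 40% (4) |
| 20% | 20% (1) | 38.0% (1.9) | 44.4% (2.2) | 50.3% (2.5) | 59.0% (3.0) | 80% (4) |
| 50% | 50% (1) | 72.9% (1.5) | 80.0% (1.6) | 86.0% (1.7) | 93.8% (1.9) | 100% (2) |

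At p = 5% to 20% and rho = 0.3 to 0.7, the ratio runs from 1.9 to 3.3.

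**3. In counts (assumed).** Take 2 of 30 reacting at each treatment: 2/30 = 6.7% in every by-visit table, and 2 × 4 = 8 reactions in all. The number of different subjects affected can be:

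- 2 (6.7%) if they are the same subjects each time;
- about 5.5 expected at rho = 0.5;
- about 7.2 expected under independence;
- 8 (8/30 = 26.7%, exact 95% CI 12.3% to 45.9%) if nobody reacts twice.

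**4. Where the factor of 4 does not apply.** Section 4.2.3 lists Visits 6 and 7 for prolonged effects, while Section 8.1 implies five occasions (start of Visits 3, 4 and 5, then Visits 6 and 7). The diary gives 7 × 4 = 28 daily ratings per symptom. The bound of 4 is for scores taken once per treatment.

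**The case against.** Several points on the other side have force.

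- **The by-visit reading is partly inferred.** The time-point wording in Section 10.2.1 belongs to the means and ranges; the sentence on counts does not repeat it. The reading rests on the denominator rule in Section 10.1, which allows exceptions. None is indicated for tolerability or VAS, so the reading stands.
- **Marked reactions are not hidden.** A reader might infer that means made up mostly of zeros would bury them. The plan does not support that: counts by category and the maximum are both planned. Only the subject-level total is missing.
- **Fourfold is not the expected size.** A reader might take it so. The same face is treated repeatedly at the same planned settings (Section 6.3), which favors repeat reactors, although settings may be lowered for tolerance, which works the other way. Section 9.2.2 treats mild to moderate transient erythema as expected; if a score of 2 is common, a ratio of 4 is impossible.
- **Stopping treatment does not erase a reaction.** A subject who leaves after a bad reaction still counts at the visit where it was scored. Such a record is lost only through the removal rule in Section 10.1.
- **A per-treatment percentage is a valid quantity.** It matches the visit-by-visit layout of Section 4.2.3. The raw data go to the sponsor, so worst scores could be derived later. That is true, but the cut-off would then be chosen with the results in view.

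**Conclusion.** The gap is real and modest. The plan will show that marked reactions occurred and how often at each treatment, but not how many treated subjects had one over the series. For immediate reactions, the missing share is between 1 and 4 times the per-treatment percentage. A factor of about 2 to 3 is plausible at assumed shares of 5% to 20% with assumed correlation of 0.3 to 0.7. Equal shares at each treatment and complete series are also assumed. The documents give no rates or correlations, so they do not support a claim that the risk will be understated fourfold, or by any particular amount; they support only that the planned tables cannot tell these cases apart. No primary or secondary effectiveness conclusion depends on this. It should be changed because it concerns a stated safety endpoint and the data are already being collected.

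**What to change.** Add to Section 10.2.1:

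- **Skin responses (0–3).** For each response, with immediate scores, later-visit scores and diary ratings kept separate, derive each subject's worst observed score over the series. Report the number and percent, with exact 95% CI, of all treated subjects whose worst score is 2 or more, and 3.
- **Population.** Use all treated subjects, with no removal because of an adverse event, and state that this table departs from the removal rule in Section 10.1. Show how many subjects had incomplete series, since their worst observed score can only be a minimum.
- **Pain.** Report each subject's worst VAS score in the plan's own VAS categories. Section 10.2.1 refers to categories but gives no limits, so fix them before analysis. Cut-offs of 2 and 3 belong to the 0–3 scales and would count low pain as an event on a 0–10 scale.
- **Labels.** Score 3 is called marked in Section 8.1 and severe in the Appendix F diary; align the wording.

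Keep the by-visit tables as supportive. The cost is a few lines of SAP text and one more table, with no new data. The headline percentages will be less favorable, or at best unchanged.

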#### 10.2.2 Additional Analysis

Additional analysis will be provided as following:

For IQIS (0-4), the mean score will be compared to a constant value of 0 to test the null hypothesis that there is no improvement after the product use, using the method described in the SAP table.

For GAIS and subject satisfaction data, a binomial (sign) test will be performed to test if the proportion of the combined designated favorable responses (Very Much Improved, Much Improved, and Improved for GAIS; Very Satisfied and Satisfied for subject satisfaction) is equal to the combined designated unfavorable responses.

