#### 7.2 Investigator Evaluations Quartile Improvement Score

Treating Investigators will compare:

- 1. Baseline photographs to one-month post treatment.
- 2. Baseline photographs to three-months post treatment.

A Quartile Improvement Scale will be used to individually score each category: (a) fine wrinkles, (b) skin texture, (c) dyschromia/pigment, (d) skin radiance, (e) pore size and (f) overall appearance.

Investigator Quartile Improvement Score				
Rating	Percentage (%)	Score		
No Improvement	0%	0		
Minor/Mild Improvement	1%-25%	1		
Moderate Improvement	26%-50%	2		
Marked Improvement	51%-75%	3		
Very Significant Improvement	76%-100%	4		

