### 7.7 Independent Photographic Assessments

Two experienced, blinded photographic reviewers will compare 2D photographs via Canfield Scientific, Inc VISIA data access system:

- The reviewer will select between 2 sets of unmarked photos and determine which
  is baseline and one-month post treatment. Based on their selection of baseline to
  one-month post treatment the reviewer will rate improvement.
- 2. The reviewer will select between 2 sets of unmarked photos and determine which is baseline and three-months post treatment. Based on their selection of baseline to three-months post treatment they will rate improvement.

A Quartile Improvement Scale will be used to individually score each category: (a) fine wrinkles, (b) skin texture, (c) dyschromia/pigment, (d) skin radiance, (e) pore size and (f) overall appearance.

Blinded Investigator Quartile Improvement Score			
Rating	Percentage (%)	Score	
No Improvement	0%	0	
Minor/Mild Improvement	1%-25%	1	
Moderate Improvement	26%-50%	2	
Marked Improvement	51%-75%	3	
Very Significant Improvement	76%-100%	4	

If the incorrect order is selected that grouping will not be used to calculate improvement. The percentage of correct to incorrect will be calculated for both one-month and three-month assessments.

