#### 10. STATISTICS

### 10.1 Statistical Analysis Populations and Demographics

The intent-to-treat (ITT) population will be the primary population for all statistical analyses. The ITT population will include all subjects who received treatment, participated in at least 1 post-baseline evaluation, and were not otherwise disqualified.

Subjects may be removed from the analysis in the case of an AE, SAE, noncompliance, or Investigator decision. The reason for any subject(s) excluded from an analysis population will be documented in a note to file and included in the study report.

Demographic data and baseline characteristics, including age, gender, ethnicity, Fitzpatrick skin type, Glogau rating, and Fitzpatrick wrinkle & elastosis scale rating, will be summarized according to the analysis population for all subjects. For continuous variables, descriptive statistics including number of subjects (N), mean, median, standard deviation (SD), minimum (MIN) and maximum (MAX) values will be presented. For categorical variables, the count and percentage of each category will be provided. The denominator for all percentages will be the number of subjects with non-missing data at the given visit for each respective study treatment, unless otherwise indicated.

The sample size determination of this study is based on the Sponsor's recommendations to quantify the effectiveness and safety of the CLEAR + BRILLIANT TOUCH® diode laser 1440-nm and 1927-nm Laser in the context of this study. Power calculations were performed based on estimates for expected mean change and variance in overall appearance at 3 months as rated by the Investigator using the Quartile Improvement Scale from study 12-133-CBP-F ('Evaluation of the skin after treatment with the Clear + Brilliant 1927-nm wavelength laser by means of the VISIA-CA Imaging System'). The power calculations demonstrated a sample size of 25 has greater than 95% power to reject the null hypothesis (change from baseline=0) for the primary efficacy endpoint. Thus, up to 30 subjects will be enrolled to account for potential drop-out.

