#### **Statistical Analysis Plan Table**

Evaluation	Change from baseline	Notes/Interpretation
Investigator	The mean score (0-4) will	Significantly greater than 0
Quartile	be compared to the	indicates improvement.
Improvement	constant 0, using Wilcoxon	
Score	signed rank test	
SAEs	NA	Zero or low number of SAEs is
		favorable
Tolerability	NA	Lower score indicates better
parameters		tolerability
VAS	NA	Lower score indicates better
		tolerability
Biopsy parameters	NA	Descriptive statistics only
Individual	NA	A binomial test (sign test) P value
response data		will be provided. A higher
(GAIS and		percentage of combined favorable
satisfaction)		responses with a significant P
		value indicates positive subject
		perceptions of the test material.
Blinded	The mean score (0-4) will	Significantly greater than 0 indicates
Investigators	be compared to the	improvement.
	constant 0, using Wilcoxson	
	signed rank test	

All statistical tests will be 2-sided at significance level alpha=0.05 unless specified otherwise. *P* values will be reported to 3 decimal places (0.000).

No multiple testing corrections will be considered in the study. Statistical analyses are performed using SAS software version 9.4 (SAS Statistical Institute). The statistical results will be sent to the Sponsor along with raw data in a Microsoft Excel document at completion of the study.

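### The signed rank test for the primary endpoint compares an improvement-only 0–4 score with 0, so it can reject only in favour of the device; the exploratory blinded score test has the same form

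*Combined protocol and SAP*

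**What the plan says.** - **Scale.** Section 7.2: "A Quartile Improvement Scale will be used to individually score each category". There are six categories, the last being overall appearance. The levels run from 0 (no improvement, 0%) to 4 (76% to 100%). No level lies below 0.
- **Test.** Section 10.2.2: "the mean score will be compared to a constant value of 0 to test the null hypothesis that there is no improvement". The SAP table compares the score with the "constant 0, using Wilcoxon" signed rank test and reads a result "Significantly greater than 0" as improvement. The text after the table adds: "All statistical tests will be 2-sided at significance level alpha=0.05 unless specified otherwise". SAS 9.4 is named, but not the procedure, the handling of zeros, or an exact or approximate p value.
- **Blinded read.** The SAP table repeats the same comparison for the blinded 0–4 score ("constant 0, using Wilcoxson" signed rank test). Section 7.7 first removes pairs: "If the incorrect order is selected that grouping will not be used to calculate improvement". It also reports the percentage of correct to incorrect orderings, with no test attached.
- **Power.** Section 10.1 claims more than 95% power at 25 subjects against a null of zero change from baseline. The inputs come from an earlier study's overall-appearance scores; their mean and variance are not given.
- **Control.** Section 4.1: there is none.

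**The concern.** A signed rank test weighs positive differences against negative ones. When the score cannot fall below the reference value, the negative side is always empty. The test is then two-sided in name only: the unfavourable tail cannot be reached whatever the faces look like. It is also the only inferential test planned for the primary endpoint, and the SAP table attaches the conclusion of improvement to it.

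At stake is what a significant p value would mean. It would show that some subjects were scored above 0 by the treating, unblinded investigator. It would not weigh those subjects against any who looked worse. The blinded read, which Section 10.2.3 offers as the protection against bias, uses the same one-directional comparison on a subset already selected for correct ordering.

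**Working it through.** **Inputs.** Two-sided alpha 0.05 (text after the SAP table); scores 0 to 4 (Sections 7.2 and 7.7); 25 evaluable subjects and up to 30 enrolled (Section 10.1). The SAP does not say which category or composite is tested, so I assume one score per subject, such as overall appearance. The 6-of-30 data set and the rates of worsening below are illustrations, not figures from the documents.

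**1. The plan's own power figure.** It cannot be reproduced without the mean and SD. Working backwards, 95% power at n=25 needs a mean/SD of about 0.75 (one-sample t test). For the exact signed rank test with zeros dropped, it needs a probability of about 0.375 that a subject scores above 0, since P(Bin(25, 0.375) ≥ 6) is about 0.95. Nothing here shows the claim to be wrong.

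**2. How few non-zero scores suffice.** With zeros dropped and all k remaining values positive, the exact two-sided p is 2 × 0.5^k: 0.0625 for k=5 and 0.031 for k=6. Neither n nor the size of the scores enters. The rule also holds for the maximum or mean of the six categories. On a maximum-of-six reading, six non-zero ratings among 30 × 6 = 180 (3.3%) are enough.

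**3. Range over versions: six subjects at 1 and 24 at 0** (mean 0.20, median 0).
- Normal approximation, zeros dropped, ties corrected: z = √k = √6 = 2.449.
- Zeros split between the signs: the 24 zeros hold ranks 1 to 24 (sum 300, half to each sign), and the six scores of 1 have midrank 27.5. W+ = 150 + 6 × 27.5 = 315; its mean is 30 × 31/4 = 232.5; its variance is 30 × 31 × 61/24 = 2363.75 without tie correction, or 2363.75 − 287.5 − 4.375 = 2071.875 with it. So z = 82.5/√2071.875 = 1.812 or 82.5/√2363.75 = 1.697.

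| Version | p for 6 of 30 | Fewest scores of 1 for p<0.05, n=30 |
|---|---|---|
| Approximate, zeros dropped | 0.014 | 4 (p=0.0455) |
| Exact, zeros dropped | 0.031 | 6 |
| Approximate, zeros split, ties corrected | 0.070 | 7 (p=0.039) |
| Approximate, zeros split, no tie correction | 0.090 | 8 (p=0.029; 7 gives 0.052) |

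The same data pass or fail according to a choice the SAP leaves open. The proportion improved is 6/30 = 20%, exact 95% CI 7.7% to 38.6%.

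**4. What a worse level would change.** With scores of +1 and −1 only, the exact signed rank p is a binomial p on the non-zero scores. Six better and none worse gives 0.031; one worse gives 0.125; two worse, 0.289; ten worse, 0.45. If raters had to enter worsening as 0 (the documents do not say), all four cases would give 0.031 on the planned scale.

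**5. Blinded read.** Suppose 15 of 30 pairs are ordered correctly, which is chance (binomial p=1.00). Among those 15, six scores of 1 and nine of 0 give p=0.031 (exact, zeros dropped), 0.028 (zeros split, ties corrected) or 0.014 (approximate, zeros dropped).

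**The case against.** Much of the picture is already planned. Section 10.2.1 gives the mean, median and counts per rating, so a reader of the 6-of-30 case would see a median of 0 and 24/30 = 80% rated as not improved. The GAIS in Section 7.6 has worse levels and a sign test. Section 8.1 has investigators score pigment change, scarring and other skin effects. In the blinded read, a worsened face can be misordered, and the ordering percentage is reported. The signed rank test stands under the heading of additional analysis, the endpoint's stated output is a percent change, and no study-success rule hangs on the p value. All of this stands and limits the harm. It does not repair the test, because none of these items enters it.

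Three stronger readings are tempting and are not supported:
- A reader might infer that the missing worse level is what stops the p value from separating a small improved minority from a general benefit. That is a general limit of any test against zero: six at +1, 24 at 0 and none worse gives 0.031 on a signed scale too.
- A reader might infer that the power above 95% is false. It may well be right; it is power against this null, and its inputs are not shown.
- A reader might infer that worsening is expected or concealed. The documents give no rate of worsening and provide other places to record it.

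**Conclusion.** The concern holds and should be fixed. As written, the primary endpoint's only inferential test is one-directional, and worsening cannot count against the device. That conclusion follows from the scale and the test alone and needs no assumption. The size depends on the version: six subjects above 0 suffice in the exact test with zeros dropped, and about four to eight scores of 1 across the versions at n=30, taking one score per subject. The blinded score test, which is exploratory, has the same form and can be significant when ordering is at chance. Because the descriptive results would show how many improved, the consequence is a p value that adds little to them, not a hidden result.

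**What to change.** 1. **Signed score.** In Section 7.2 add levels −1 to −4 that mirror the improvement bands, and apply the signed rank test to the signed score. Worsening then counts. This does not change p when nobody is rated worse, and it does not remove the unblinded rater's bias. The scale would no longer exactly match the earlier study's, or the one in Section 7.7. Power can fall: at n=25, with scores of +1, 0 or −1 and 60% better (assumed), exact power is at least 99.9% with 0% worse, 87% with 10% and 55% with 20%; at n=30 the last two are 93% and 64%. The figure in Section 10.1 must therefore be rechecked for the signed score, with the mean and SD stated.
2. **Effect estimate.** Report the proportion with an overall-appearance score of 1 or more at 3 months, with an exact 95% CI, as the main effect estimate. This, not the signed scale, addresses the small-minority problem. Any minimum proportion is for the sponsor to set beforehand.
3. **Blinded read.** Replace the score test with a two-sided exact binomial test, per reviewer, of the correct-order proportion against 50%, using all pairs. Report the score among correctly ordered pairs descriptively. State that photo position is randomised within each pair, because the 50% null needs it. Significance needs 18/25 or 21/30 correct (p=0.043 each; 17/25 gives 0.108 and 20/30 gives 0.099). Power at a true 80% correct is 89% or 94%. The order test shows a detectable change, not its size.
4. **While amending,** name the category or composite tested, the zero handling, and whether p is exact or approximate.

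The cost is protocol and SAP wording, one case report form scale and one changed exploratory test. No extra visits or readers are needed.
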